10.3 Assessments of Adverse Events

Each adverse event will be assessed for the following criteria:

10.2.1 Severity

Category	Definition
Mild	The adverse event does not interfere with the volunteer's daily routine, and does not require intervention; it causes slight discomfort
Moderate	The adverse event interferes with some aspects of the volunteer's routine, or requires intervention, but is not damaging to health; it causes moderate discomfort
Severe	The adverse event results in alteration, discomfort or disability which is clearly damaging to health

10.2.2 *Causality*

The assessment of relationship of adverse events to the pulse oximetry measurement is a clinical decision based on all available information at the time of the completion of the measurement. The following categories will be used to define the causality of the adverse event:

Category	Definition
Definitely:	There is clear evidence to suggest a causal relationship, and other possible contributing factors can be ruled out.
Probably:	There is evidence to suggest a causal relationship, and the influence of other factors is unlikely
Possibly	There is some evidence to suggest a causal relationship (e.g. the event occurred within a reasonable time after administration of the trial medication). However, the influence of other factors may have contributed to the event (e.g. the patient's clinical condition, other concomitant events).
Unlikely	There is little evidence to suggest there is a causal relationship (e.g. the event did not occur within a reasonable time after administration of the trial medication). There is another reasonable explanation for the event (e.g. the patient's clinical condition, other concomitant treatments).
Not related	There is no evidence of any causal relationship.
Not Assessable	Unable to assess on information available.

10.2.3 *Expectedness*

Category	Definition
Expected	An adverse event that is classed in nature as serious and which is consistent with the information about the pulse oximeter and probe listed in the Investigator Brochure or clearly defined in this protocol.
Unexpected	An adverse event that is classed in nature as serious and which is not consistent with the information about the pulse oximeter and probe in the Investigator Brochure

10.2.4 *Seriousness*

Seriousness as defined for an SAE in section 10.1. Collection, recording and reporting of adverse events (including serious and non-serious events and reactions) to the sponsor will be completed according to the sponsor's guidelines.

10.3 Procedures for recording and reporting Serious Adverse Events

All serious adverse events will be recorded in the medical notes. The CI will submit a serious adverse event notification and send this to the sponsor within one working day of becoming aware of the event. The CI will respond to any SAE queries raised by the sponsor as soon as possible.

All SUSARs will be notified to the sponsor immediately (or at least within one working day). The sponsor will notify the REC and MHRA of all SUSARs. SUSARs that are fatal or life-threatening will be notified to the MHRA and REC within 7 days after the sponsor has learned of them. Other SUSARs must be reported to the REC and MHRA within 15 days after the sponsor has learned of them.

10.4 Annual progress reports

An annual progress report (APR) will be submitted to the REC within 30 days of the anniversary date on which the favourable opinion was given, and annually until the trial is declared ended. The CI will prepare the APR.

10.5 Reporting Urgent Safety Measures

If any urgent safety measures are taken the CI and Sponsor shall immediately and in any event no later than 3 days from the date the measures are taken, give written notice to the MHRA and the relevant REC of the measures taken and the circumstances giving rise to those measures.

10.6 Notification of Serious Breaches to GCP

A “serious breach” is a breach which is likely to effect to a significant degree:

- (a) the safety or physical or mental integrity of the subjects of the study
- (b) the scientific value of the study

The study sponsor will notify the licensing authority in writing of any serious breach of the conditions and principles of GCP in connection with the study or the protocol relating to the study, within 7 days of becoming aware of that breach. The sponsor will be notified immediately of any case where the above definition applies during the study.

11 Data management and quality assurance

11.1 Confidentiality

All data will be handled in accordance with the UK Data Protection Act 1998. All data collected will not bear the subject’s name or other personal identifiable data. A study assigned patient and healthcare provider ID will be used for identification.

11.2 Data collection tools

Data collection will be done using Android tablets for the observational data and with paper forms for the usability questionnaire. These data collection tools have been developed for the purpose of this study, but are based on the Systems Usability Scale and tools developed by the Malaria Consortium for evaluating pulse oximeter performance. The tools have been piloted with the study team and will be piloted with end-users prior to implementation.

It will be the responsibility of the investigator to ensure the accuracy of all data entered in the electronic form.

11.3 Data handling and analysis

All observational data will be collected using ODK Collect on an Android tablet. Validation rules will be in-built in the ODK Collect form on the tablet (i.e. not allowing input of invalid values). The tablet will be password protected and the data uploaded to a secure server, which only study personnel can access, with password and username protection. Data will be downloaded as a CSV file and converted to a Stata file. All electronic data will be stored on secure University servers, accessed on password protected computers.

The usability questionnaire will be collected on paper. Quantitative answers will be entered into an Access database and exported into a Stata file. Qualitative data will be analysed directly from the paper forms, with specific quotes transcribed into Microsoft Word. All paper data will be stored in locked cabinets in the Lifebox office.

12 Record keeping and archiving

Archiving will be authorised by the Sponsor following submission of the end of study report. All paper data will be archived in a locked cabinet in the Lifebox offices, and all databases and electronic data will be stored on secure University and Lifebox servers.

The CI is ultimately responsible for the secure archiving of essential trial documents and the study database. All essential documents will be archived for a minimum of 5 years after completion of the study. Destruction of essential documents will require authorisation from the Sponsor.

13 Statistical Considerations

13.1 Outcomes

13.1.1 Primary outcomes

The primary outcome in the study is the proportion of measurements in which a stable oxygen saturation reading was obtained within 60 seconds of placing the pulse oximetry probe by all healthcare providers. This will be measured in both expert users and healthcare providers and the results pooled

13.1.2 Secondary outcomes

Secondary study outcomes include:

- The difference in the time to a stable oximetry reading for expert users compared to healthcare providers in different settings
- The difference in the time to a stable oximetry reading for children of different age
- Qualitative evaluation of the usability of the probe and oximeter
- The fit of the probe on the child's hand or foot
- The child's tolerance for the probe

13.2 Sample size and recruitment

13.2.1 Sample size calculation

To calculate 95% of measurements being stable within 60 seconds (as per the target product profile) with 2.5% precision and 95% confidence intervals requires 292 measurements. This is calculated using the standard formula to calculate a sample size for estimating a proportion:

$$n \geq (Z^2 \times p(1-p))/e^2$$

(Z = confidence interval; p = expected true proportion; e = desired precision, half the desired CI width)

$$n \geq (0.95^2 \times 0.95(1-0.95))/0.025^2$$

$$n \geq 292$$

The FDA HF/UE guidance and IEC 62366 state that at least 15 participants should be included from each identified user group interacting with the device. We intend to include 17 trained healthcare workers from a high-income setting, and 17 from each of two low-income settings where there is a high burden of disease in children, and where the Lifebox pulse oximeter is supplied. Each end-user will take 12 measurements (3 from each of four different age-group stratifications of children). This gives a total of 204 measurements from each user-type in each setting. In addition to our pooled primary analysis, this will give us enough power to conduct pooled stratified analyses by site and age group.

The primary outcome will be a pooled analysis from all the participating sites, stratified by expert user and healthcare provider. Studying this number of healthcare workers will give the study sufficient power to undertake sub-group analysis by site and by age of the children assessed.

A summary of the stratified analyses is presented in the table below:

Primary Analysis	GOSH	Malawi	Bangladesh	Total (2 sites)	Total (3 sites)
Healthcare providers	204	204	204	408	612
Expert users	204	204	204	408	612
All measures	408	408	408	816	1,224
Sub-Analysis					
Neonates (HCW + expert)	102	102	102	204	306
Infants (HCW + expert)	102	102	102	204	306
Toddler (HCW + expert)	102	102	102	204	306

1. For an online calculator:

<http://epitools.ausvet.com.au/content.php?page=1Proportion&Proportion=0.95&Conf=0.95&Precision=0.025&Population>

Child (HCW + expert)	102	102	102	204	306
----------------------	-----	-----	-----	-----	-----

*shaded cell indicates sufficient power

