The secondary objective is to provide further description of the 'usability' of the redesigned oximeter and probe in children aged 0-59 months by healthcare workers, to assess how well children tolerate the probe, and the difference in time to a stable oximetry reading for expert users and healthcare workers in different settings, or for different ages of children.

Type of study: Mixed methods observational usability testing

Study design and methods: This observational usability testing involves three types of data collection from three sites in the UK, Malawi and Bangladesh. This protocol relates specifically to the UK testing at Great Ormond Street Hospital.

Expert usability testing: the probe and oximeter will be used by an expert on 204 stable children (i.e. not physiologically unstable or admitted to a high-dependency or intensive care unit) of different ages and with varying illness states. Children will be purposefully recruited from inpatient wards to meet age criteria by a clinical researcher. Following consent, an oxygen saturation measurement will be done by the expert user. An independent observer will note the condition of the child, along with other key demographic, performance and clinical features and the time to successful measurement of oxygen saturation.

Healthcare provider usability testing: the probe and oximeter will be used by healthcare providers on healthy or mild systemically ill patients (i.e. with a normal oxygen saturation, i.e. >94%). Children will be purposefully recruited from inpatient wards to meet age requirements by a clinical researcher and pre-screened for their oxygen saturation. 17 healthcare workers will be assessed for their performance with the prototype probe. Each HCW will undertake an oxygen saturation measurement on 12 children (maximum 204 children at Great Ormond Street Hospital). An independent observer will note the condition of the child, along with other key demographic, performance and clinical features and time to successful measurement of oxygen saturation.

Usability Questionnaire: HCW will be asked to complete a usability questionnaire to collect quantitative and qualitative feedback about the oximeter and probe usability. The questionnaire will be completed following the usability testing by all the healthcare providers.

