13.2.2 Planned recruitment rate

We estimate that for 3 healthcare providers to take 12 oxygen saturation measurements will take up to one day. The expert will be taking oxygen saturation readings in parallel. Therefore, allowing for healthcare provider availability and patient turn-over on the inpatient wards, we anticipate recruitment to take a maximum of 3 weeks.

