13.3 Statistical analysis plan

13.3.1 Primary outcome analysis

We will calculate the proportion of readings that meet the target product profile requirement of 95% stable readings within 60 seconds. Differences in the proportion of successful readings will be compared between the expert and healthcare providers, between different age groups of children, and between the UK, Bangladesh and Malawi. This will be done using χ^2 tests. All descriptive analyses will be done using Stata 14.

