13.3.2 Secondary outcome analysis

We will describe the time to stable reading, looking at the median time and inter-quartile range. We will compare these descriptive statistics between patient age groups, expert and healthcare provider participants, and with measurements from Malawi and Bangladesh. We will look for statistical differences between these sub-groups using t-tests. Descriptive analysis of the observational data on usability, including correct positioning and number of re-positions of the probe, will be conducted. Qualitative questionnaire data will be analysed using an inductive thematic approach.

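### Sample size, χ² tests and t-tests treat readings as independent although they cluster by user, so site and user-type tests over-reject; the number of experts is not stated

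*Combined protocol and SAP*

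**What the plan says.** Section 13.2.1 sizes the study for one proportion: 95% success "with 2.5% precision and 95% confidence intervals requires 292 measurements". It adds: "This is calculated using the standard formula to calculate a sample size for estimating a proportion". That formula assumes a simple random sample of readings.

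The same section describes how the readings arise: "Each end-user will take 12 measurements (3 from each of four different age-group stratifications of children". With 17 workers at each of three sites, that is 204 worker readings per site and 612 in all. It then claims enough power for analyses by site and age group.

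For GOSH experts the wording is singular. The Summary (Section 2) says "the probe and oximeter will be used by an expert on 204 stable children", and Section 13.2.2 says "The expert will be taking oxygen saturation readings in parallel". Section 4 speaks of expert users in the plural. Section 13.2.1 arrives at 204 readings per user type from 17 × 12, which could be read as 17 experts per site. No count is given for Malawi or Bangladesh.

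Section 13.3.1 compares success between user types, age groups and countries: "This will be done using χ^2 tests". Section 13.3.2 does the same for time to a stable reading: "We will look for statistical differences between these sub-groups using t-tests". Neither section, nor the sample size section, mentions correlation within a user.

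**The concern.** Readings by one person share that person's skill. The plan itself gives reasons to expect differences between people. Sections 5 and 7 recruit workers purposefully for a range of oximetry experience, and under Section 5 the timing ends when the user calls it, so each user's own threshold for a stable waveform enters all of that user's times.

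Site and user type are attributes of the user, not of the reading. A test that counts readings can therefore report a site or user-type difference that is only a difference between the individuals sampled. The expert-versus-worker time difference across settings is a listed secondary outcome (Section 13.1.2), and the site and user-type comparisons of success sit in the primary analysis section. If GOSH has one expert, that person's skill cannot be separated from being an expert, and no later model can repair this.

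**Working it through.** **Inputs.** From Section 13.2.1: p = 0.95, half-width e = 0.025, 17 workers per site, 12 readings each (3 per age group), 204 readings per user type per site, 612 per user type over three sites. From Sections 2 and 13.2.2: apparently one expert at GOSH. The ICC is not in the documents; 0.02, 0.05 and 0.10 are assumed.

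**The plan's figure.** n = Z²p(1−p)/e² = 1.96² × 0.95 × 0.05 / 0.025² = 291.96, i.e. 292. This reproduces under independence. (The printed line has 0.95 where Z = 1.96 belongs and would give 68.6; the result of 292 is right.)

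**What the ICC values mean.** The between-user SD of true success is √(ICC × 0.0475). In a beta model this is 3.1, 4.9 and 6.9 percentage points, with 0.8%, 4.8% and 8.8% of users truly below 85% success.

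**Precision.** Design effect DE = 1 + (m − 1) × ICC, with m = 12 for a worker and m = 204 for a lone expert. Effective n = 612/DE. Worker half-width = 1.96 × √(0.0475 × DE/612).

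| ICC | 0.02 | 0.05 | 0.10 |
|---|---|---|---|
| Workers: DE | 1.22 | 1.55 | 2.10 |
| Workers: effective n | 502 | 395 | 291 |
| Workers: half-width, points (1.7 if independent) | 1.9 | 2.1 | 2.5 |
| Experts, one per site: DE | 5.06 | 11.15 | 21.3 |
| Experts, one per site: effective n | 121 | 55 | 29 |

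Effective n falls to 292 at ICC = (612/292 − 1)/11 = 0.0996 for workers, but at (612/292 − 1)/203 = 0.0054 for one expert per site.

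A pooled age cell has 306 readings, 14 above 292: 153 from workers (3 per user) and 153 from experts. With one expert per site (51 per user per cell), effective n is 306/(1 + 26 × ICC), which is below 292 once the ICC exceeds about 0.002. With 17 experts per site it is 306/(1 + 2 × ICC), below 292 beyond about 0.024.

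**Error rates by simulation.** Proportions: beta-binomial, p = 0.95, 40,000 replicates (20,000 for the age test), no true difference. Time: normal random user effect on log time, two sites of 17 × 12. With ICC = 0 all these tests reject about 5% of the time, so the simulations are calibrated.

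| Nominal 5% test | 0.02 | 0.05 | 0.10 |
|---|---|---|---|
| Three-site χ², workers | 8% | 14% | 24% |
| t-test of log time, two sites, workers | 8% | 11% | 17% |
| Expert v worker χ², pooled, one expert per site | 27% | 44% | 59% |
| Same, 17 experts per site | 8% | 12% | 18% |
| GOSH only, one expert, claim about experts in general | 26% | 44% | 59% |
| GOSH only, that expert taken as a fixed user | 6% | 8% | 12% |
| Age-group χ², workers | 4% | 4% | 3% |

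An ordinary Wald 95% interval for the worker proportion covers 91%, 88% and 81% (about 94% at ICC 0). The age test is not inflated because each worker measures all four age groups equally.

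**Check of the remedy.** In the same simulations, a logit-scale cluster interval with t on 50 df covers 94.9%, 95.1% and 94.6%. A user-level F-test for site on the 51 per-worker proportions (2 and 48 df) rejects 4.7%, 4.7% and 4.2%.

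**The case against.** - **Unknown ICC.** The size of the inflation depends on a figure the documents do not give. At ICC 0.01 the worker site test rejects only about 6.7% of the time. This stands as a limit on magnitude. But an ICC of exactly zero is hard to defend here, and at 0.01 the test with one expert per site already rejects 17% of the time.
- **The largest figures stack assumptions.** They need one expert at each site, and experts who vary as much among themselves as purposefully varied workers. With expert ICC at half the worker value the pooled contrast rejects 18%, 32% and 45%; at a quarter, 12%, 22% and about 33%; with no expert variation, 6%, 8% and 12%. This stands: the size of that problem is not fixed. Every case is still above 5%.
- **Raw time.** The plan does not mention log time. With lognormal raw times and an assumed log SD of 1.0, the two-site t-test rejects about 6%, 8–9% and 13–14%; at SD 0.5 it is close to the log-time result. Inflation can be smaller than tabulated, but it remains.
- **No interval is specified.** Section 13.3.1 only calculates a proportion, so the coverage figures apply to an interval that Section 13.2.1 implies but the analysis does not name. Fair; the analysis should name one.
- **Modest weight.** Section 5 judges success by the proportion against 95%, and no decision rule rests on a χ² result or an interval. This stands, and it limits the harm to reported uncertainty and to claims about site and user type.

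**Conclusion.** The concern holds. The sample size formula and the stated tests ignore clustering by user, and nothing elsewhere in the plan handles it; stratifying by user type does not. For any ICC above zero the site and user-type tests exceed their nominal 5%. Over assumed ICCs of 0.02 to 0.10 the worker site test runs at 8–24%. The expert-versus-worker test runs anywhere from 6% to 59%, depending on how many experts there are and how much they differ.

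The point estimate is sound because planned readings per worker are equal. Pooled worker precision meets ±2.5 points up to an ICC of about 0.10, and the age test is safe. The ±2.5-point claim fails for experts as a group if there is one per site and the ICC exceeds about 0.005. That there is one expert at GOSH rests on singular wording; the number elsewhere is unknown. This should be fixed, but it does not undermine the main estimate.

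**What to change.** 1. **Worker proportion:** report a cluster-robust 95% interval with user as the cluster, on the logit scale, with t on clusters minus 1 df.
2. **Site comparison in workers:** replace the χ² test with a user-level F-test on the 51 per-worker proportions. Mixed-effects logistic regression, or GEE with a small-sample correction, is an alternative. Its behaviour should be checked first, because at p = 0.95 some 54–67% of workers would score 12 out of 12 (ICC 0 to 0.10).
3. **Time comparisons between sites and user types:** replace the t-tests with the matching user-level analysis or a mixed model with a user term.
4. **Sample size section:** restate worker precision with DE = 1 + 11 × ICC over a stated ICC range.
5. **Experts:** state the number per site and record an ID for each before data collection.
6. **If experts are one or very few per site:** report their results and the expert-versus-worker contrast descriptively, as the performance of those users, with no χ² p-value and no ±2.5-point claim for experts in general. If they are many, use the same user-level model.

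The age χ² test may stay.

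**Cost.** SAP wording and a few lines of Stata. Section 11.1 already provides the worker identifier: "A study assigned patient and healthcare provider ID will be used for identification". Only an expert ID must be added, and no more participants are needed. The price is wider intervals than a reading-level analysis gives, and no formal expert-versus-worker test if experts are few.

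### The planned age analyses mix expert and provider readings half and half, and no expert-versus-provider contrast within each setting is specified, so a provider-only shortfall in one subgroup would be diluted

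*Combined protocol and SAP*

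**What the plan says.** - **Layout of readings (13.2.1).** "Each end-user will take 12 measurements (3 from each of four different age-group stratifications of children"). With 17 providers per site, "This gives a total of 204 measurements from each user-type in each setting".
- **Primary analysis (13.2.1, and similarly section 5).** "The primary outcome will be a pooled analysis from all the participating sites, stratified by expert user and healthcare provider". The table accordingly has separate provider and expert rows, 204 each at GOSH, Malawi and Bangladesh, above a combined row of 408 per site. Section 13.1.1, however, says that the results of the two user types are pooled.
- **Age sub-analyses (13.2.1 table).** All four rows combine the user types, starting with "Neonates (HCW + expert"), at 102 per site and 306 over three sites. There is no age row by user type.
- **Tests (13.3.1).** Proportions are compared by chi-squared test between experts and providers, "between different age groups of children, and between the UK, Bangladesh and Malawi". Section 13.3.2 lists the same three factors for time to reading, with t-tests. Neither section names a comparison of user types within a site or an age group.
- **Question asked (13.1.2, also section 4).** "The difference in the time to a stable oximetry reading for expert users compared to healthcare providers in different settings".

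**The concern.** Section 5 defines success as the 60-second target being met by any level of healthcare worker. Section 3.3 wants it met in a range of children and at sites with different training. Section 3.1 names neonates and infants as the patients for whom the reusable probe needs improving. The informative cells are therefore frontline providers by age and by site.

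In the age rows, half of each such cell consists of expert readings. If providers struggle with neonates and experts do not, the neonatal figure averages the two. The same happens by site if the site test is run on the merged readings. The expert-provider gap at each site, which the secondary question points to, has no stated analysis. It would be left to choices made after the data are seen.

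**Working it through.** **Inputs from the plan.** Target 95%, precision 2.5 points, 17 providers per site, 12 readings each (3 per age group), 204 readings per user type per site, three sites.

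**Assumptions not in the plan.** Two-sided 5% level; independent readings; providers at 85%, 87.5% or 90% in the affected group; experts, and providers elsewhere, at 95%.

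**1. The plan's own figure.** The sample size is stated as "with 2.5% precision and 95% confidence intervals requires 292 measurements". 1.96² × 0.95 × 0.05 / 0.025² = 291.95, so 292 is reproduced. (The printed substitution shows 0.95 in place of 1.96; that would give 68.6.)

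**2. Cell sizes.** 17 × 12 = 204. 17 × 3 = 51 provider readings per age group per site; 51 + 51 = 102; 3 × 102 = 306 = 153 + 153. Site totals are 204 + 204 = 408. All match the table.

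**3. Dilution.** Merged proportion = (expert + provider)/2.
- Experts 95%, providers 90%: 92.5%. A 5-point shortfall shows as 2.5.
- Experts 95%, providers 85%: 90%. A 10-point shortfall shows as 5.
- Experts 98%, providers 92%: 95.0%. The shortfall against the target disappears.

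**4. Power, one site against another.** Power = Φ{[|p₁ − p₂| − 1.96√(2p̄(1 − p̄)/n)] / √[(p₁(1 − p₁) + p₂(1 − p₂))/n]}.
- Merged, 95% v 90%, n = 408: (0.05 − 1.96 × 0.01844)/0.01836 = 0.755, power 77%.
- Provider-only, 95% v 85%, n = 204: (0.10 − 1.96 × 0.02970)/0.02929 = 1.43, power 92%.

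| Providers in the affected group | Site v site, merged (408) | Site v site, providers (204) | Age v age, merged (306) | Age v age, providers (153) |
|---|---|---|---|---|
| 90% | 31% | 48% | 25% | 38% |
| 87.5% | 56% | 77% | 45% | 64% |
| 85% | 77% | 92% | 65% | 83% |

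**5. Power across four age groups.** Simulated chi-squared test on 3 degrees of freedom, providers at 85% in one group and everything else at 95%: about 72% merged (306 per group) and about 91% provider-only (153 per group).

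**6. The opposite case.** If both user types fall from 95% to 90% at one site, merging has 77% power (n = 408) and provider-only 48% (n = 204).

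**7. Would an interaction test recover the loss?** User type × site on the difference scale, 204 per cell.
- 10-point provider-only drop: SE = √[(3 × 0.0475 + 0.1275)/204] = 0.0364; 0.10/0.0364 − 1.96 = 0.79, power 78%.
- 5-point drop: SE = √[(3 × 0.0475 + 0.09)/204] = 0.0338; power 32%.

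The merged site test gives 77% and 31%, so the interaction offers essentially no gain. The gain comes from provider-only estimates.

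**8. Precision after splitting.** Half-width = 1.96√(0.0475/n): 3.45 points at 153 and 2.99 at 204, against 2.44 at 306 and 2.11 at 408. Neither 153 nor 204 reaches 292. Clustering inflates the variance by about 1 + (12 − 1)ρ for a provider's full set of readings and 1 + (3 − 1)ρ within an age group. The plan gives no ρ.

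**The case against.** The strongest reply is that the plan already separates user types where it matters most. Sections 5 and 13.2.1 stratify the primary analysis, and the table gives 204 provider and 204 expert readings at every site. That stands, and it rules out three stronger readings that a reader might infer.

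- **That the site comparison certainly uses merged readings.** Section 13.3.1 does not say which row of the table the site test uses. The merge is inferred from silence, and the stratified rows point the other way. Because 13.1.1 speaks of pooling user types, the documents leave it unsettled.
- **That the expert-provider question in different settings cannot be estimated.** The cells exist and an overall user-type comparison is planned. What is missing is a stated contrast within each setting. The wording in 13.1.2 could also mean experts against providers who work in different settings, which summaries by user and site would answer.
- **That experts vary least by age or setting, so halving is the rule.** Nothing in the documents supports this. Experts measure children with varying illness states, while providers measure healthy or mildly ill children with saturation above 94%. Case mix could make expert results vary more.

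Two further points stand. Merging serves the plan's precision target: 306 meets 292 and 153 does not. And the power figures concern the 60-second proportion, whereas the 13.1.2 question concerns time to reading. Section 13.3.2 has the same one-factor structure, so the gap in specification carries over, but its size for time has not been shown.

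The reply does not remove the explicit mixing in all four age rows or the absence of a within-setting contrast in 13.3.

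**Conclusion.** The concern holds as a gap in the subgroup analyses, and closing it is a cheap improvement. The age rows mix user types one to one by design, and the site comparison may do so. For a 10-point drop confined to providers, the cost is a fall in power from 92% to 77% between two sites and from about 91% to about 72% across four age groups.

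The result depends on experts staying at the reference rate; only then is the dilution exactly half. It also depends on the assumed success rates and on independent readings. Correlation within a provider would lower the provider-only power below the figures shown. If both user types drop together, the merged analysis is the better one, so both views are needed. The primary result stratified by user type is not undermined.

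**What to change.** 1. In 13.3.1 and 13.3.2, keep the merged results. Add age and site results within healthcare providers, and the expert-minus-provider difference with a 95% CI at each site. Do this for both the 60-second proportion and time to reading.
2. Use intervals that allow for the 12 readings per provider being clustered.
3. Treat a user type × site term as optional and descriptive, since it has no useful power advantage over the merged test.
4. Split each age row of the 13.2.1 table by user type. State that 153 per age group and 204 per site fall below 292, with half-widths of about 3.5 and 3.0 points at 95% before clustering.
5. Reconcile 13.1.1 (pooled over user types) with section 5 and 13.2.1 (stratified), and say which readings the site test uses.
6. Add a caution on the expert-provider contrast. The two groups measure different case mixes, and few experts may contribute per site (section 2 and 13.2.2 refer to a single expert at GOSH), so the contrast may partly reflect patients or individuals and not user type.

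The cost is SAP wording and a little more analysis. No extra children or data items are needed, because user type, site and age are already design factors. The price is wider intervals in the provider-only cells and more results to report.
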